9.9 Serious adverse events and adverse events

Frequencies of AEs, SAEs and SUSARs will be described per intervention arm for total number of events, per solicited event, and for unsolicited events. Events will be grouped using the MedDRA classification system. Frequencies will be compared using logistic regression analysis and reported as OR with 95% CI.

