Objective: To determine the impact of BCG vaccination on the incidence of clinically relevant respiratory infections or COVID-19 in vulnerable elderly.

Study design: An adaptive multi-center double-blind randomized placebo-controlled trial.

Study population: 5,200 to 7,000 vulnerable elderly, defined as ≥ 60 years of age and being discharged from hospital in the last 6 weeks, having a chronic somatic comorbidity, undergoing major surgery, or attending a thrombosis care service. Patients with contraindications to BCG vaccination as stipulated in the Summary of Product Characteristics (SPC) and patients with a history of COVID-19 will be excluded.

Intervention: Participants will be randomized between intracutaneous administration of BCG vaccine (Danish strain 1331) or placebo (0.1ml 0.9% NaCl) in a 1:1 ratio.

Main study parameters/endpoints: The trial has an adaptive primary endpoint. Based on accrual of the two endpoints, the primary endpoint will be either (a) COVID-19 or (b) clinically relevant respiratory tract infection (RTI) requiring medical intervention, potentially including COVID-19 episodes. The other will be declared secondary endpoint. Other secondary endpoints include: all SARS-CoV-2 infections (including asymptomatic infections), influenza infection, RTI (all infections regardless of medical intervention), RTI-related hospital admission, COVID-19 related hospital admission, pneumonia, mental, physical and social functioning, serious adverse events and adverse events, and death.

Nature and extent of the burden and risks associated with participation, benefit and group relatedness: Based on previous experience in published and ongoing randomized controlled trials in adults and elderly, the risks of BCG vaccination are considered negligible. Vaccination could cause local pain, suppuration and scarring at the site of injection. The size of the trial will ensure rapid availability of results that can inform policy-making during the ongoing pandemic and may be of benefit for participants that received no intervention, as well as individuals who did not participate in the trial.

3 Sample size

This is an event driven trial. To demonstrate a 50% reduction of the incidence of the primary endpoint with a two-sided alpha of 0.05, 67 endpoints are needed for 80% power and 90 events for 90% power.

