The primary study parameter will be analyzed as a time-to-event outcome using a Cox proportional hazards analysis. The randomization date will be considered T=0 and the symptom onset date of the primary endpoint (or in case of COVID-19 the date of positive test result if that occurs earlier) will be considered the event time. Censoring time of participants with no event will be the last date of follow-up. The analysis will be adjusted for the stratification variables (hospital and age category) and for strong prognostic factors*. The result will be reported as the number of episodes per arm, number of patient-years of follow-up per arm, and hazard ratio (HR) with 95% CI.

* For COVID-19 there are no prognostic factors that can be measured at enrolment so only stratification variables will be used. For clinically relevant RTI: presence of the following (groups of) comorbidities: cardiovascular disease or stroke, chronic pulmonary disease (COPD, asthma or other chronic pulmonary disease), diabetes mellitus, solid organ or hematological malignancy, moderate to severe chronic renal disease.

9 Analysis of the secondary endpoints

Please refer to the protocol for definitions of each endpoint.

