9.8 Mental, physical and social functioning at 6 months

The change in Katz-Activities of Daily Living score, Lawton Activities of Daily Living score and EQ5D quality of life score between baseline and end of study will be analysed using linear regression. The stratification variables (hospital and age category) will be added as covariates to the model. The results will be reported as differences in change of score with 95% confidence intervals.

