9.10 Cumulative incidence of all-cause 6-month mortality

Analysis will be the same as for the primary endpoint COVID-19.

10 Analysis of the exploratory endpoints

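### Section 9.9 compares adverse events without hospital and age category, the variables every other modelled comparison adjusts for; the interval then over-covers and a little power to detect harm is lost (minor)

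*SAP*

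**What the plan says.** The primary Cox analysis (SAP section 8) includes the strata: "The analysis will be adjusted for the stratification variables (hospital and age category) and for strong prognostic factors". For COVID-19 the footnote there drops the prognostic factors, "so only stratification variables will be used". Sections 9.1 to 9.7 and 9.10 take over that model by reference: "Analysis will be the same as for the primary endpoint COVID-19". Section 9.8 (functioning) puts the strata into its linear model explicitly: "The stratification variables (hospital and age category) will be added as covariates to the model".

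Section 9.9 (adverse events and serious adverse events) is the exception: "Frequencies will be compared using logistic regression analysis and reported as OR with 95% CI". It names no covariates and gives no reason for leaving them out. It also does not say that the model is unadjusted. The SAP sets no power, margin or precision target for adverse events.

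**The concern.** When allocation is balanced within strata, differences in risk between strata cannot create a chance difference between the arms. A logistic model with treatment alone does not know this and counts the between-stratum variation as sampling noise. Its standard error is then too large for the crude log odds ratio it estimates, and the test rejects less often than its nominal 5%.

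For an efficacy endpoint, that is conservative in the usual sense. For a safety comparison, under-rejection makes a real excess of events slightly harder to see. Section 5.4 declares significance when the 95% interval excludes no effect. Adverse events are listed among the secondary endpoints, so the coverage of this interval bears on a stated decision rule.

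**Working it through.** **The plan's own figure.** The SAP has no figure for the safety comparison. Its only calculation concerns efficacy: "with a two-sided alpha of 0.05, 67 endpoints are needed for 80% power and 90 events for 90% power", for a 50% reduction. The Schoenfeld formula, 4(z₀.₉₇₅ + z_power)²/(ln 0.5)², gives 4 × (1.96 + 0.842)²/0.480 = 65.4, so 66 events, and 4 × (1.96 + 1.282)²/0.480 = 87.5, so 88. The stated figures are in line with this, but they say nothing about adverse events.

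**Inputs.** From the SAP: 1:1 allocation, two-sided 5%, "5,200 to 7,000 vulnerable elderly", strata of hospital and age category. Assumed, because the SAP does not give them: 6,000 participants, 20 hospitals, 3 age categories with an odds ratio of 1.5 per step, exact balance within strata, event risk 20% or 40%, and a hospital log-odds SD of 0.4, 0.8 or 1.2. The ratio of odds between the 90th and 10th percentile hospital is exp(2 × 1.2816 × SD), which is about 2.8, 7.8 and 22 for these SDs.

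**Formula.** Let p be the risk in a stratum and P the overall risk, with no treatment effect and n per arm.
- Model variance of the crude log odds ratio: 2/[nP(1−P)].
- True variance under balanced strata: 2·E[p(1−p)]/[nP²(1−P)²].
- Ratio of true to model SE: r = √{E[p(1−p)]/[P(1−P)]}, which is below 1 whenever p varies.
- True type I error: 2Φ(−1.96/r).
- SE of the stratified log odds ratio relative to the crude one: about 1/r, which is above 1.

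**Numbers in.** Simulation gave r from 0.97 (SD 0.4) to 0.90 (SD 1.2) at 20% risk, and from 0.97 to 0.87 at 40%.
- r = 0.97: 1.96/0.97 = 2.02, type I error 4.3%.
- r = 0.90: 1.96/0.90 = 2.18, type I error 2.9%.
- r = 0.87: 1.96/0.87 = 2.25, type I error 2.4%.

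**Simulation**, 20,000 trials per setting, unadjusted Wald against Mantel-Haenszel:

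| Event risk (OR for power) | Hospital SD | Type I error, unadjusted | Type I error, stratified | Power, unadjusted | Power, stratified | Loss (points) |
|---|---|---|---|---|---|---|
| 20% (1.2) | 0.4 | 4.3% | 4.7% | 80% | 81% | 1 |
| 20% (1.2) | 0.8 | 3.8% | 5.0% | 74% | 78% | 4 |
| 20% (1.2) | 1.2 | 2.9% | 4.8% | 66% | 73% | 7 |
| 40% (1.17) | 0.4 | 4.3% | about 4.9% | 82% | 83% | 1 |
| 40% (1.17) | 0.8 | 3.4% | about 4.9% | 75% | 80% | 5 |
| 40% (1.17) | 1.2 | 2.4% | about 4.9% | 65% | 74% | 9 |

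The formula and the simulation agree. Smaller repeat runs of 4,000 trials at 20% risk gave unadjusted type I errors of 4.2% to 4.6%, 4.2% to 4.5% and 2.8% to 3.5% for the three SDs.

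**Less common events.** At 5% risk the loss is about 1 point, except at SD 1.2, where runs gave between 2 and about 4 points. At 2% risk it is 0.1 to 0.7 points for SD 0.2 to 0.8, and 1.5 points at SD 1.2.

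**Width of the interval.** The mean Mantel-Haenszel SE of the log odds ratio exceeded the crude one by 1% to 11% at 20% risk and by 2% to 15% at 40%, as 1/r predicts (1/0.90 = 1.11; 1/0.87 = 1.15).

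**The case against.** A reader might infer that the safety intervals are too wide and that adding the strata would narrow them. For the odds ratio this is wrong. Adjustment moves the estimate from a marginal to a conditional odds ratio, further from 1, and its SE on the log scale grows. With 5,200 participants and a conditional odds ratio of 1.5, a logistic model with hospital and age terms had an SE 0.1% to 5% larger than the crude model, while the crude analysis saw a marginal odds ratio of 1.44 to 1.50. That objection stands against any promise of a narrower interval. It does not remove the over-coverage, because the two SEs belong to different estimands, and the relevant comparison is each SE with the sampling error of its own estimate.

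A reader might also infer that real harms would be materially missed. The SAP does not support this. The larger losses need between-hospital odds ratios of about 8-fold or 22-fold, and nothing in the document points to such variation. The mix of eligibility routes does not establish it either, since those routes are not the strata. At SD 0.2 the loss is 0.6 points at 20% risk and 0.8 at 40%. In the odds ratio 1.5 calculation, with hospital SD up to 0.6, adjusting gained at most 1 point of power at 2% and 5% risk (for example 91.2% against 92.2%). At 20% risk both methods were near 100%, so that calculation says nothing about small effects on common events. Rare serious events are where the concern is weakest.

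Two further points are fair. Section 9.9 is silent about covariates rather than explicitly unadjusted, so the omission may be one of drafting. And a logistic model with many hospital terms can be unstable for sparse events, which is a reason to choose a stratified method over simply adding covariates.

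**Conclusion.** The inconsistency is real: section 9.9 is the only modelled comparison of the arms in the SAP that leaves out hospital and age category. Read as a treatment-only model, it gives an interval that over-covers and a test with true type I error below 5%. It is therefore valid but somewhat inefficient, in the direction that matters for safety.

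The cost is about 1 to 2 points of power for common events under moderate hospital variation, 4 to 5 points at SD 0.8, and 7 to 9 points only at SD 1.2. For events at or below 5% it is about 1 point or less in most settings. All of this assumes that randomisation was balanced within these strata, as the term stratification variables implies; exact 1:1 balance, as simulated, is the case most favourable to the concern. Event rates, hospital count and heterogeneity are assumptions throughout. Severity: minor.

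**What to change.** In section 9.9, state that the outcome is whether a participant had at least one event of the given type, and that the arms are compared by an analysis stratified for hospital and age category: Mantel-Haenszel odds ratio with 95% CI (Robins-Breslow-Greenland variance), with the Mantel-Haenszel risk difference and its CI beside it. This tolerates strata with few or no events. It also settles the unit of analysis: section 9.9 describes total event counts, but logistic regression needs one yes/no outcome per participant.

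The cost is one sentence and a few lines of code, with no new data. The SAP should state the downside: the odds ratio becomes conditional on stratum, lies slightly further from 1, and has a slightly wider interval on the log scale than the crude one. If the team prefers an unadjusted comparison, section 9.9 should say so and give the reason.

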9.10 Cumulative incidence of all-cause 6-month mortality

Analysis will be the same as for the primary endpoint COVID-19.

10 Analysis of the exploratory endpoints

10.1 Interaction between BCG and other vaccines

Primary and secondary analyses will be stratified for status of vaccination with other vaccines at baseline, in particular influenza and pneumococcal vaccine. If the data allow, an additional analysis will be performed using a time-varying influenza and pneumococcal vaccination status with interaction to determine the impact of receiving these vaccines *after* BCG vaccination.

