4.2 Analysed populations

The primary analysis population is the intention-to-treat (ITT) population in which participants will be analysed according to the random allocation.

Subgroups:

We will explore the presence of interaction between BCG and other vaccines, in particular influenza and pneumococcal vaccine.

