5.4 Inferential statistics

Effect estimates for primary and secondary endpoints will be reported with 95% CI. Effect estimates with a 95% CI not including the zero-effect will be considered statistically significant.

6 Disposition of participants and conduct of the study

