7.1 Demographics / baseline characteristics

The following data will be described for included participants by treatment arm and for the total population:

VARIABLE	DERIVATION	STATISTICAL METHOD *
Age (years)	Self-reported at baseline	Median (IQR) or mean (sd) ¹
Gender	Self-reported at baseline: Male/ Female	n/N (%)
History of BCG vaccination	Self-reported at baseline: Yes/No	n/N (%)
Age at BCG vaccination	Self-reported at baseline	Median (IQR) or mean (sd) ¹ among those with reported history of BCG vaccination
BMI	Self-reported at baseline	Median (IQR) or mean (sd) ¹
Receipt of influenza vaccination in past season (2019-2020 or 2020-2021 depending on date of enrolment)	Self-reported at baseline: Yes/No	n/N (%)
Receipt of pneumococcal vaccination in past or current season	Self-reported at baseline: Yes/No	n/N (%)
Receipt of other vaccinations in past 12 months	Self-reported at baseline (open question) ²	n/N (%) for each reported vaccination
History of hypertension	Self-reported at baseline: Yes/No	n/N (%)
History of cardiovascular disease	Self-reported at baseline: Yes/No	n/N (%)
History of stroke	Self-reported at baseline: Yes/No	n/N (%)
History of diabetes mellitus	Self-reported at baseline: Yes/No	n/N (%)
History of COPD	Self-reported at baseline: Yes/No	n/N (%)
History of asthma	Self-reported at baseline: Yes/No	n/N (%)
History of other pulmonary diseases	Self-reported at baseline: Yes/No and open question ²	n/N (%) for each reported pulmonary disease if deemed relevant
History of moderate to severe renal disease	Self-reported at baseline: Yes/No	n/N (%)
History of solid organ or haematological malignancy	Self-reported at baseline: Yes/No	n/N (%)
History of dementia (diagnosed by physician)	Self-reported at baseline: Yes/No	n/N (%)
History of other chronic diseases	Self-reported at baseline: Yes/No and open question ²	n/N (%) for each reported disease if deemed relevant
Medication use	Self-reported at baseline	Listing of medication on group level based on ATC code system
Clinical Frailty Scale	Self-reported at baseline	Median (IQR)

History of smoking	Self-reported at baseline. Options are: - Never smoked - Ever smoked - Current smoking	n/N (%) for all categories
Smoking of household member	Self-reported at baseline: Yes/No	
Alcohol use	Self-reported at baseline: Yes/No, quantity in categories	n/N (%) per category
History of allergic rhinitis	Self-reported at baseline: Yes/No	n/N (%)

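### Interaction between BCG and baseline vaccination is to be explored, but only stratified analyses are planned, with no contrast between strata

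*SAP*

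**What the plan says.** Section 4.2 of the SAP states the aim: "We will explore the presence of interaction between BCG and other vaccines, in particular influenza and pneumococcal vaccine".

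Section 10.1, whose title names this interaction, gives the method in two parts:

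- Vaccination status at baseline: "Primary and secondary analyses will be stratified for status of vaccination with other vaccines at baseline".
- Vaccination during follow-up: "If the data allow, an additional analysis will be performed using a time-varying influenza and pneumococcal vaccination status with interaction". The purpose given is "to determine the impact of receiving these vaccines" after BCG.

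The significance rule in section 5.4 is: "Effect estimates with a 95% CI not including the zero-effect will be considered statistically significant". The Cox model in section 8 adjusts for hospital and age category, plus comorbidities for clinically relevant RTI. It has no vaccination term. The data needed are listed in section 7.1: "Receipt of influenza vaccination in past season" and "Receipt of pneumococcal vaccination in past or current season".

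**The concern.** An interaction is a difference between treatment effects, here the ratio of the BCG hazard ratio in vaccinated participants to that in unvaccinated participants. For baseline vaccination the plan produces the two components and stops. The ratio can be derived from the two HRs and their intervals, but the SAP does not say that it will be.

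On the natural reading of the stratified analysis, each stratum gets its own HR and interval, and section 5.4 supplies a label for each, significant or not. The difference, which is the quantity section 4.2 asks about, gets neither estimate nor interval. On a less likely reading, the Cox baseline hazard is stratified by vaccination status; that yields one common BCG effect and no information on interaction.

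The exploratory question would then be settled by looking at the stratum results side by side. One significant and one non-significant stratum can easily be taken as evidence that another vaccine modifies the effect of BCG when it does not.

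**Working it through.** **1. What the text provides**

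| Vaccination status | Analysis in 10.1 | Contrast between strata |
|---|---|---|
| At baseline | Stratified primary and secondary analyses | None named |
| After BCG (time-varying) | Model with interaction, if the data allow | Yes, conditional |

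Sections 5.4 and 8 do not fill the first row.

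**2. Inputs**

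From SAP sections 2 and 3: a 50% reduction (taken as HR 0.5), two-sided alpha 0.05, 1:1 allocation, and "67 endpoints are needed for 80% power and 90 events for 90% power". The SAP gives no share of events by vaccination status, so splits from 50:50 to 80:20 are assumed.

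**3. The plan's own figures**

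Schoenfeld's formula, events = 4(z₁ + z₂)² / (ln HR)²:

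- 80% power: 4 × (1.960 + 0.842)² / 0.693² = 65.3, so 66 events (SAP: 67).
- 90% power: 4 × (1.960 + 1.282)² / 0.693² = 87.5, so 88 events (SAP: 90).

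The power is 81.0% with 67 events and 90.8% with 90. The stated numbers reproduce closely.

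**4. If strata were compared by significance, with no true interaction**

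For a stratum with d events, m = |ln HR| × √d / 2, and the chance of significance is p = Φ(m − 1.96) + Φ(−m − 1.96). The chance that exactly one of two strata is significant is p₁(1 − p₂) + p₂(1 − p₁).

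Example with HR 0.5, 67 events, 50:50: d = 33.5, m = 0.693 × 5.788 / 2 = 2.006, p = 0.518. Exactly one: 2 × 0.518 × 0.482 = 0.499.

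Example with HR 0.5, 67 events, 80:20: p = 0.718 and 0.245. Exactly one: 0.718 × 0.755 + 0.245 × 0.282 = 0.611.

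| Common HR | Exactly one significant (67 or 90 events, 50:50 to 80:20) |
|---|---|
| 0.5 | 46% to 63% |
| 0.6 | 43% to 55% |
| 0.7 | 29% to 37% |
| 0.8 | 18% to 21% |
| 1.0 | about 10% |

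A direct test of interaction at the 5% level is falsely positive in 5% throughout. At HR 0.7 the most likely pattern is that neither stratum is significant (59% to 68%).

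**5. What a direct contrast would deliver**

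The standard error of the log ratio of HRs is √(4/d₁ + 4/d₂). The 95% CI runs from the ratio divided by exp(1.96 × SE) to the ratio multiplied by it. The ratio detectable with 80% power is exp(2.80 × SE).

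| Events | Split | SE | CI factor | Power for a two-fold ratio | Ratio detectable with 80% power |
|---|---|---|---|---|---|
| 67 | 50:50 | 0.489 | 2.6 | 29% | 3.9 |
| 67 | 80:20 | 0.611 | 3.3 | 21% | 5.5 |
| 90 | 50:50 | 0.422 | 2.3 | 38% | 3.3 |
| 90 | 80:20 | 0.527 | 2.8 | 26% | 4.4 |

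**The case against.** The strongest reply is that this is an omitted sentence, not an error. Section 4.2 promises to explore, not to test. Stratum estimates with intervals are one way to explore, and the contrast can be computed from them. Nothing in the SAP says that a significant and a non-significant stratum will be read as interaction, so the figures in step 4 describe a possible misuse. Section 5.4 opens with primary and secondary endpoints, so its reach into an exploratory section is open, although section 10.1 does stratify the primary and secondary analyses. The largest percentages need the full design effect, and the 63% also needs an 80:20 split. A formal interaction term would have little power.

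Much of this stands. The percentages are conditional and must not be read as an expected error rate of the plan. The low power is real. These points limit the weight of the concern but do not remove it: the method written down does not estimate the stated target, and the same section uses an interaction model for the other question. Low power is a reason to show a ratio with its wide interval, since separate stratum labels hide that uncertainty.

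A further fair point is scope. Section 10.1 also covers endpoints analysed by linear or logistic regression (sections 9.8 and 9.9) and refers to other vaccines generally. A change to the Cox model for two vaccines leaves those untouched unless the SAP addresses them.

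**Conclusion.** The concern holds and is minor. For baseline vaccination the SAP plans no estimate of the interaction it sets out to explore. Should strata be compared by significance, a false appearance of interaction would arise in 46% to 63% of trials at the design effect, falling to about 10% when BCG has no effect, against 5% for a direct test. These figures rest on the SAP's 67 or 90 events, 1:1 allocation within strata, independent strata and assumed event splits. They apply to the primary endpoint only, because event numbers for secondary endpoints are not given. The primary conclusion is not affected.

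**What to change.** In section 10.1, add a BCG-by-baseline-influenza-vaccination term to the Cox model and, in a separate model, a BCG-by-baseline-pneumococcal-vaccination term, each with the main effect of that vaccination. Report the ratio of HRs with its 95% CI as the exploratory interaction result, labelled as low-powered. Show stratum HRs as description only, and state that strata will not be compared by significance. Say also which secondary endpoints and which further vaccines this covers.

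The cost is SAP wording and one interaction term per vaccine. Both variables are already collected at baseline (section 7.1), and neither the sample size nor the primary analysis changes. The drawback is imprecision: at 67 events the interval extends by a factor of 2.6 to 3.3 either side of the estimate, so a null result will not exclude a sizeable interaction.
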